8.3.3.3 EXPECTEDNESS

The principal investigator, [name] will be responsible for determining whether an adverse event (AE) is expected or unexpected. An AE will be considered unexpected if the nature, severity, or frequency of the event is not consistent with the risk information previously described for the study intervention.

8.3.4 TIME PERIOD AND FREQUENCY FOR EVENT ASSESSMENT AND FOLLOW-UP

The occurrence of an adverse event or serious adverse event may come to the attention of study personnel during study visits, interviews of a study participant presenting for medical care, or upon review by a study monitor.

All adverse events not meeting the criteria for a serious adverse event will be captured on the case report form. Information to be collected includes event description, time of onset, assessment of severity, relationship to study intervention, and time of resolution/stabilization of the event. All adverse events occurring while on study will be documented appropriately regardless of relationship, and followed to resolution or until the participant no longer wants to be contacted.

Any medical condition that is present at the time that the participant is first seen will be considered as baseline and not reported as an adverse event. However, if the study participant's condition deteriorates at any time during the study, it will be recorded as an adverse event.

Changes in the severity of an adverse event will be documented to allow an assessment of the duration of the event at each level of severity to be performed. Adverse events characterized as intermittent require documentation of onset and duration of each episode.

The principal investigator, [name], will be responsible for the recording of all reportable events with start dates occurring any time after informed consent is obtained until resolution or until the participant no longer wants to be contacted. At each study visit, the investigator will inquire about the occurrence of adverse events.

8.3.5 ADVERSE EVENT AND SERIOUS ADVERSE EVENT REPORTING

The study will record, assess, categorize, and report all adverse events and serious adverse events as per the reporting requirements of the Northwell Health Human Research Protection Program and the Food and Drug Administration, as applicable.

8.3.6 REPORTING EVENTS TO PARTICIPANTS

If an adverse event or serious adverse event is observed, the participant will be notified immediately upon discovery in person or by phone call. In addition, participants will be told of any new findings that may change their decision to continue to participate.

If incidental findings that are deemed clinically-significantly are discovered, the participant will be notified and recommended to seek further clinical evaluation and care.

8.3.7 REPORTING OF PREGNANCY

- If an individual becomes pregnant during the course of the study, she will be withdrawn from the study, as early pregnancy may potentially impact measurements.

8.4 UNANTICIPATED PROBLEMS

8.4.1 DEFINITION OF UNANTICIPATED PROBLEMS (UP)

An unanticipated problem involving risks to participants or others includes any incident, experience, or outcome that is considered:

- Unexpected in terms of nature, severity, or frequency given the research procedures and participant population being studied;
- Related or possibly related to participation in the research; and
- Suggests that the research places participants or others at a greater risk of harm than previously known or recognized.

8.4.2 DEFINITION OF UNANTICIPATED ADVERSE DEVICE EFFECTS (UADE)

An unanticipated adverse device effect is any serious adverse effect on the health and/or safety or any life threatening problem or death caused by, or associated with, the device, if that effect, problem, or death was not previously identified in nature, severity, or degree of incidence in this study; or any other unanticipated serious problem associated with a device that relates to the rights, safety, or welfare of subjects (21 CFR 812.3(s)). An event will not be considered related to the device when it is the result of a pre-existing medical condition or medication.

A device malfunction is the failure of a device to meet its performance specifications or other performance as intended. Performance specifications include all claims made in the labeling for the device. The intended performance of a device refers to the labeled use for which the device is labeled.

8.4.3 UNANTICIPATED PROBLEM REPORTING

The study will record, assess, and report all unanticipated problems involving risks to subjects or others and unanticipated adverse device effects as per the reporting requirements of the Northwell Health Human Research Protection Program and the Food and Drug Administration, as applicable. The report will include a detailed description of the event, incident, experience, or outcome; an explanation for its occurrence and assessment; and a corrective action plan.

8.4.4 REPORTING UNANTICIPATED PROBLEMS TO PARTICIPANTS

If an unanticipated problem involving risks to subjects or others or unanticipated adverse device effects occur, the participant will be notified immediately upon discovery in person or by phone call, if deemed necessary. Upon reporting to the appropriate regulatory agencies, the study team will implement the approved corrective action plan. This plan will outline the mechanism and time course for notifying study participants.

9 STATISTICAL CONSIDERATIONS

9.1 STATISTICAL ENDPOINTS AND HYPOTHESES

Our primary outcome measures are expected to be 75% for recruitment, 90% for retention, and 80% for adherence. We calculated two-sided 95% confidence intervals for one proportion using the Clopper-Pearson method with scenarios varying the expected percent (0.70 and 0.95) in order to estimate precision given a sample size of 30. The lower confidence level will be used to inform recruitment, retention, and adherence planning in the future RCT.

9.2 SAMPLE SIZE DETERMINATION

Table 2. Precision of estimated proportions given a sample size of 30			
Estimated Proportion	Lower CL	Upper CL	Width
0.70	0.506	0.853	0.347
0.75	0.559	0.889	0.330
0.80	0.614	0.923	0.309
0.85	0.673	0.953	0.281
0.90	0.735	0.979	0.244
0.95	0.803	0.996	0.193

CL=confidence level

9.3 STATISTICAL ANALYSES

9.3.1 ANALYSIS OF THE EFFICACY ENDPOINTS

Protocol Number: 21-0640

February 1, 2022

Planned Data Analysis. The purpose of the pilot study is to determine whether an RCT evaluating the efficacy of taVNS on mental health outcomes is feasible, acceptable, and satisfactory for WTC responders with PTSD. The total sample size for the Aim 2 pilot trial is 30 World Trade Center Health Program responders with PTSD. Primary endpoints are based on feasibility. Specifically, recruitment, retention, and adherence, will be measured. Recruitment is defined as the percent of eligible responders who meet all study criteria and were recruited and consented to be in the study. Retention is defined as the percent of participants who completed both baseline and 6-week measures. Adherence is defined as the percent of participants who used taVNS 15 minutes a day once a day for 8 weeks. Secondary endpoints of acceptability include participant satisfaction and ability to complete the various mental health, blood draw and biologic measures with limited refusal, limited non-response, and within acceptable amounts of time. Tertiary endpoints include mental health and biologic measures. Please see the outcomes measures section for detailed definitions.

All measures will be described using frequency/percent or mean (SD) as appropriate, overall and by taVNS and sham group, with corresponding 95% confidence intervals to interpret the precision of the estimates. Median and interquartile range may also be used if discrete data are skewed. For the tertiary outcomes measuring mental health and biologic data, descriptive statistics for each time point, as well as differences over time (baseline to 8 week follow-up), will be calculated. Differences in biologic (non-inflammatory) outcomes only will be assessed from the first time point at baseline and the last time point at 8 weeks for long-term effects. Within-subject correlation of acute and long-term measures will be reported. Estimates and variances at each time point will be used to generate hypotheses and calculate effect sizes for a larger future RCT. Since effect sizes observed in pilot studies are crude, due to the small sample size, they may not be indicative of the true difference in the larger population and will be interpreted with caution.

We will also use results to generate hypotheses regarding potential mechanisms of action including the various inflammatory, neural, and cardiovascular changes that correlate with treatment outcomes. We will explore whether the impact of taVNS on PTSD symptoms is mediated by biologic measures of physiological reactivity and inflammatory markers.

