6 STUDY INTERVENTION

6.1 STUDY INTERVENTION(S) ADMINISTRATION

6.1.1 STUDY INTERVENTION DESCRIPTION

Aim 1: A Focus Group Discussion Guide will be finalized by the research team prior to recruitment (see Appendix 1 for example blank focus group data collection instrument). It will include questions to understand the relevance, feasibility and acceptability of: (1) using a taVNS device generally, (2) using it as treatment for PTSD, (3) the implementation protocol of the device, (4) the pilot study protocol (including the methodology details, timing, and both self-report, clinical, and biological assessments), and (5) the appropriateness of outcome measures. The estimated duration for the focus group is \approx 90 minutes. Drs. [name] and [name] will co-lead the focus group and the coordinator will take notes, write the minutes, and audio-record the session. [name] and/or [name] will demonstrate the device. Individuals will have the opportunity to handle the devices and there will be sanitizing wipes to be used in between. The focus group will be transcribed for qualitative analyses.

Aim 2:

Table 1. Aim 2 Outcome Measures	
Primary Outcome Measures (measured at 8 weeks)	
FEASIBILITY	
Recruitment	
-% responders who meet criteria 1-3 who accepted to come in for the CAPS interview (goal=33%)	
-% eligible responders who meet criteria 1-4 of those who came in for the CAPS interview (goal=66%)	
-% eligible responders who meet all criteria and were recruited and consented (goal = 75%)	
Retention	
-% participants who complete baseline and 8-wk measures (both survey and biological measures) (goal = 90%)	
Adherence	
-% participants who used taVNS 15 min/day once a day for 8 weeks (21 hours total) (goal=80%)	
Secondary Outcome Measures (measured at 8 weeks)	
ACCEPTABILITY	
Collection of Measures	
-Time (minutes) to fill out questionnaires (goal =<30 min)	
-Missing data from questionnaires: % items complete on the baseline and 8-wk self-report surveys (goal=90%)	
-Time (minutes) to collect biological data and blood draw (goal=10 min at baseline and 10 minutes at follow-up)	
-Rate of refusal of biologic measurements/blood draw (goal=5% refusal)	
Satisfaction	
-taVNS Intervention Study satisfaction survey (Adapted from Bakken et al.) (range=12-60; goal=100%-with score >47 among intervention group) ¹⁰⁰	
Tertiary Outcome Measures (measured at baseline and 8 week follow-up)	
Mental health symptoms (assessed to indicate signals for hypothesis generation)	

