Responders will then be instructed to use the device once a day, every day at home, for 15 minutes intervals over 8 weeks. The devices have a safety feature where they cannot be used for more than the intended timepoints daily and the stimulation parameter will be set by the investigator and cannot be altered by the participant. The date and time stamp of each use will be recorded on the application. The application only assesses usage/compliance and has no ability to capture any personal or other information. All phones containing the Nesos application is collected at the end of the study. Responders are requested to come in 8 weeks post-baseline and the same measures will be recorded again (self-report, biological and blood draw; see Table 1).

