8 STUDY ASSESSMENTS AND PROCEDURES

8.1 EFFICACY ASSESSMENTS

Aim 2: Primary Outcome Measure: Feasibility will be evaluated using criteria suggested by Leon⁹⁹: 1) rates of recruitment (per month), 2) adherence to the taVNS intervention, 3) 8-week retention, and 4) duration and completion rate of study assessments. Feasibility is defined as the ability to recruit 75% of eligible, approached, participants and to demonstrate intervention adherence and retention rates of 70% each (Table 1). **Secondary Outcome Measure:**

Protocol Number: 21-0640

February 1, 2022

Acceptability will be evaluated by assessing: 1) time to completion of questionnaires, 2) percentage of missing data from questionnaires, 3) time to completion of the biological data and blood draw, 4) rate of refusal of biologic measurements and blood draw, and 5) score on the taVNS Satisfaction and Usefulness Questionnaire¹⁰⁰ (Table 1). **Tertiary Outcome Measures** include potential taVNS endpoint measures. At the baseline and 8 week follow-up visits, validated self-report MH measures, including assessments of PTSD,⁹⁴ anxiety,¹⁰¹ depression,¹⁰² sleep,¹⁰³ and the CAPS interview⁹⁵ (at screener and follow-up) will be administered. To examine **potential mechanisms of action** and any acute and longer-term change in these mechanisms, the biological measures will be administered at baseline 10 minutes before using the device, again one time at the 8-week follow-up visit. Blood will be drawn to assess markers of inflammation before using the device, after using the device, and again at the 8 week follow-up visit. This allows us to collect data to understand potential acute and long-term effects. These tertiary outcome measures and potential mechanisms of action will be used to inform the

design of a future, RCT to evaluate taVNS efficacy. Measurement quality, amount of missingness or non-response, length of measurement collection, and costs will be assessed. These measures will also be used to provide parameter estimates for power calculations for a future RCT (Table 1). We will also use the preliminary efficacy results from this pilot to generate hypotheses regarding potential mechanisms of action including the various inflammatory, neural and cardiovascular changes that correlate with treatment outcomes

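### Primary adherence measure sets no minimum share of sessions: read as written, one missed day counts as non-adherence, and the 70% or 80% target is unlikely to be met unless daily use is near perfect or misses fall in a few people

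*Protocol*

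**What the plan says.** Adherence is one of the primary feasibility measures of Aim 2, and the protocol defines it twice. Section 9.3.1 states: "Adherence is defined as the percent of participants who used taVNS 15 minutes a day once a day for 8 weeks". Table 1 in Section 6.1.1 counts "participants who used taVNS 15 min/day once a day for 8 weeks", adds a total of 21 hours in parentheses, and sets a goal of 80%. Section 9.3.1 refers the reader to the outcome measures for detailed definitions, but Table 1 adds no allowance for missed days.

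The instruction to participants in Section 6.1.1 is: "Responders will then be instructed to use the device once a day, every day at home, for 15 minutes intervals over 8 weeks". The same section says of the device: "The devices have a safety feature where they cannot be used for more than the intended timepoints daily". It also says that the app records the date and time of each use.

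There are two targets. Section 8.1 reads: "Feasibility is defined as the ability to recruit 75% of eligible, approached, participants and to demonstrate intervention adherence and retention rates of 70% each". The synopsis and Section 3 say the same. Section 9.1 reads: "Our primary outcome measures are expected to be 75% for recruitment, 90% for retention, and 80% for adherence", which matches the Table 1 goal. Both figures are shares of participants, not of sessions. Sections 8.1 and 9.1 add that the lower confidence limit will inform planning of the future RCT.

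**The concern.** The measure turns eight weeks of daily use into one yes or no per participant, and the protocol names no point short of full use at which the answer becomes yes. A responder with 55 of 56 sessions then falls in the same category as one who never switched the device on. The detail in the time-stamped log is lost from the primary result.

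Two decisions depend on this proportion: whether the intervention is called feasible, and what adherence rate the RCT is planned on. If use is good but not perfect, the proportion can be low although most sessions were completed. The report could then call the intervention infeasible, and the RCT could be planned on a figure that understates actual use. Near-perfect use is not a safe default here. The protocol describes a population with barriers to staying in treatment, and Section 2.1 reports that 27.9% of a local group in mental health care did not reliably attend weekly.

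**Working it through.** **Inputs from the protocol.** One 15-minute session a day for 8 weeks, so 8 × 7 = 56 sessions (Section 6.1.1). Sample size 30 (Section 9.3.1). Targets of 70% (21 of 30) and 80% (24 of 30). **Assumed:** the daily-use rate q and the clustering of misses within people. The protocol gives neither, so ranges are shown.

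**The plan's own figures.** The two-sided 95% Clopper-Pearson limits with n = 30 are 0.506 to 0.853 at 0.70 and 0.614 to 0.923 at 0.80. All six rows of Table 2 in Section 9.2 reproduce to three decimals. The precision table is correct; the issue is what is being counted.

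**Step 1. Daily use needed to reach the targets.** With independent days, the share adherent is q^56, so the q needed is target^(1/56).
- For 70%: 0.70^(1/56) = 0.9937, or 56 × 0.0063 ≈ 0.36 missed days per person in 8 weeks.
- For 80%: 0.80^(1/56) = 0.9960, or about 0.22 missed days per person.
- If the 10% whom the plan expects not to retain count as non-adherent, the retained need (0.70/0.90)^(1/56) = 0.9955 and (0.80/0.90)^(1/56) = 0.9979.

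**Step 2. Share adherent if days are independent.**

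| Daily use q | q^56 | Chance of at least 21/30 | Chance of at least 24/30 |
|---|---|---|---|
| 0.90 | 0.3% | near 0 | near 0 |
| 0.95 | 5.7% | near 0 | near 0 |
| 0.98 | 32% | 0.003% | near 0 |
| 0.99 | 57% | 10% | 0.7% |
| 0.995 | 76% | 82% | 37% |

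**Step 3. Share adherent if misses cluster in some people.** Let each person's daily-use rate follow a beta distribution with mean m and intraclass correlation ρ, with a = m(1/ρ − 1) and b = (1 − m)(1/ρ − 1). The share adherent is the beta-binomial probability of 56 out of 56.

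| Mean use m | ρ = 0.05 | ρ = 0.1 | ρ = 0.2 | ρ = 0.4 |
|---|---|---|---|---|
| 0.90 | 7% | 16% | 32% | 54% |
| 0.95 | 26% | 40% | 57% | 74% |
| 0.98 | 59% | 69% | 80% | 89% |

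Over this range, 90% mean use never reaches 70%. At 95% the 70% target is reached only with the strongest clustering shown, and 80% is not reached. At 98% both targets can be reached.

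**Step 4. The same participants under a session-share rule (illustration).** Take adherent to mean at least 80% of 56 sessions: 0.80 × 56 = 44.8, so 45 or more. With independent days, 55% qualify at q = 0.80, 99% at 0.90 and about 100% at 0.95. With clustering over the same ρ range, 83–90% qualify at m = 0.90 and 92–98% at m = 0.95.

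**Step 5. The denominator.** 56 × 15 minutes = 14 hours, not the 21 hours in Table 1. Twenty-one hours is 84 sessions, which is 84/56 = 1.5 a day. The adherence-measurement text in Section 10.1.6 gives one to two sessions a day; its data management plan and Section 10.1.8.1 give two. If 21 hours were the criterion and one session a day the schedule, nobody could qualify.

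**The case against.** The strongest reply is that the definition restates the regimen and is not a scoring rule. Neither definition mentions 56 of 56 or excludes missed days in terms. The daily requirement appears in the instruction to participants, and a scoring cut-off is often left to an analysis plan, which is not at hand. This has some force: strict scoring is the natural reading, but it remains a reading. It does not remove the problem. The protocol itself defines this primary measure in its statistics section and sends the reader to a table that repeats the same rule. If some tolerance was intended, no amount is given, and the proportion cannot be scored reproducibly from this text. The 70% and 80% figures supply no tolerance, because they count participants.

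Three stronger readings are tempting, and the documents do not support them.
- *The targets are practically out of reach, or a group using the device on 95–98% of days would be reported as non-adherent.* This follows only if days are independent. With clustered misses, the share adherent reaches 74% at 95% mean use and 89% at 98%.
- *A missed day can never be made up.* The device limits use to the intended daily timepoints, but the protocol gives that number variously as one, one to two, and two. The 21-hour total also hints at a cumulative criterion.
- *The trial will wrongly conclude infeasibility.* The analysis is descriptive, every use is logged, and nothing prevents reporting at session level. The risk comes from applying the rule as stated, and no data are lost.

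**Conclusion.** The concern holds in a bounded form. That one missed day scores the same as no use follows from the definition as written and needs no assumption about behaviour. How far this lowers the proportion does depend on assumptions. With independent days, average daily use must be about 99.4% for the 70% target and 99.6% for the 80% goal. Clustering relaxes this, but the result then turns on how misses are spread between people as much as on how much the device is used: at 95% mean use, the share adherent runs from 26% to 74% within the range examined. A proportion that moves this much at constant total use is a poor basis for a feasibility decision or a planning rate. The two targets and the conflicting session and hour statements are related faults in the same measure. They must be settled too, but settling them would not supply the missing minimum share.

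**What to change.** In Table 1 and Section 9.3.1:
- Define a participant as adherent if the app log shows at least a pre-specified share of scheduled home sessions, for example 80%, with one sensitivity cut-off. The 80% is an illustration; the protocol offers no basis for a particular value.
- Count participants who are not retained by their logged sessions over the full scheduled number.
- Report the mean or median percentage of sessions completed, overall and by arm, and carry that into RCT planning beside the proportion adherent.
- State one participant-level goal, since 70% and 80% both appear.
- Reconcile the statements on sessions per day and total hours in Sections 6.1.1, 10.1.6 and 10.1.8.1 so that the denominator is defined. This review takes no position on which schedule is right.

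The cost is small. The time-stamped log already holds the data, and the scoring rule changes nothing in how participants are treated. The downside is that a cut-off must be chosen and justified before the usage data are examined.

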Tertiary endpoints of this study include multiple mental health and biologic potential endpoints to be measured at the baseline of the pilot feasibility trial as well as at the 8-week follow-up time point. Tertiary outcome measures include potential taVNS endpoint measures. At the baseline and 8-week follow-up visits, validated self-report mental health measures, biological measures, and the CAPS PTSD interview (at screener and follow-up) will be administered. To examine potential mechanisms of action and any acute and longer-term change in these mechanisms, all biological measures will be administered at the baseline visit 10 minutes before using the device, and then again one time at the 8 week follow-up visit. These tertiary outcome measures and potential mechanisms of action will be used to inform the design of a future RCT to evaluate taVNS efficacy. We will assess measurement quality, amount of missingness/non-response, length of measurement collection, and costs. These measures will also be used to provide parameter estimates for power calculations for a future RCT.

We will also use the initial study results to understand signals that point to potential variables to include that best indicate taVNS efficacy, and potential mediators of the impact of taVNS on PTSD when implemented in a future RCT involving multiple WTCHP sites. As such, preliminary efficacy of taVNS on PTSD symptoms will be assessed.

Differences between baseline and post-treatment mental health measures will be used to generate hypotheses for a future larger RCT targeting PTSD symptoms as a primary outcome, and anxiety, depression, and sleep quality as secondary outcomes, in order to more robustly evaluate taVNS efficacy among a larger sample of WTC responders with PTSD thereby conferring greater statistical power. We will also use results from this pilot to generate hypotheses regarding potential mechanisms of action including the various inflammatory, neural and cardiovascular changes that correlate with treatment outcomes.

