6.3 MEASURES TO MINIMIZE BIAS: RANDOMIZATION AND BLINDING

Protocol Number: 21-0640

February 1, 2022

Randomization: A randomization schema will be pre-generated by the Biostatistics Unit at FIMR, using the Biostatistics Randomization Management System (BRMS) software, by a statistician not affiliated with the study. Responders will be randomly assigned in a 2:1 ratio to either taVNS or sham and given a unique randomization ID number. The randomization schema will be read into the randomization module in REDCap, a data management system that only the coordinator can access. The software will monitor the allocation progress and responder assignment.

Concealed Allocation: The coordinator will create and keep a crosswalk between participant ID, unique randomization ID number, and assignment in REDCap. Nesos Corp will use the unique randomization ID number to label the molds for fitting the device. After the fitted devices are received, the coordinator will give Nesos Corp a table with unique randomization ID number labels and assignment for Nesos Corp to designate the appropriate program to the device based on the responder's allocation. For the taVNS program, when the responder uses the app to activate the device, the taVNS will provide stimulation at a value that was calibrated to that responder. For the sham program, the device will not provide any electrical stimulation.

Blinding: Responders in the taVNS and the sham group will be blinded to their assignment. *Both groups will not be able to detect the stimulation provided* and thus, will not know which group they are in. The directions provided and the use of the application will be the same for both groups. All investigators will be blinded to participation assignment as well. Biologic outcome measures will be conducted by [name]. The CAPS will be conducted by senior study staff and oversight of self-report survey completion will be provided by the research coordinator. Only the research coordinators will not be blinded to the assignment. They will receive the allocation assignment after enrollment and will coordinate with Nesos Corp to program the devices corresponding to assignment.

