D. Potential Limitations: Ideally, the activity of deep brain structures related to relevant neural circuits would also be measured using fMRI, given their role in mediating stress and the impact that innervation of the vagus nerve has on specific brain areas, such as the Nucleus Tractus Solitarius. Given the scope of this pilot feasibility study, however, it is not possible to conduct fMRIs on 30 participants. This is something that will warrant further exploration in the next phase of study- an RCT with a large sample size powered to detect differences in outcomes and mediational relationships. In addition, the inclusion of participants staying in their current MH treatment may dilute the ability to test the effects of taVNS. However, given that this is a pilot feasibility study and effect sizes will only be used for hypothesis generation, treatment dilution is less of a concern. We are now, however, examining the role of current treatment in an exploratory manner as its potential role as a likely covariate in future RCT analyses (or as a variable on which to block randomize). Finally, should distancing requirements of COVID-19 continue to be a concern in the beginning of the study period, the study team can easily pivot to implementing the focus group and screening procedures over secure video conference, and the survey measures can be completed electronically via a secure email link. Fitting for the taVNS devices as well as biologic measurements can be conducted quickly and safely with all appropriate precautions taken regarding PPE provision and use for both the study staff and the participant.

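### Mediation is to be explored with biology and symptoms both measured at week 8, so a biomarker that merely follows symptom change can pass for a mediator

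*Protocol*

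**What the plan says.** Section 9.3.1, after saying that results will generate hypotheses about changes that correlate with outcome, adds: "We will explore whether the impact of taVNS on PTSD symptoms is mediated by biologic measures of physiological reactivity and inflammatory markers". Section 8.1 (Hypothesis Generation) says the same. No mediation model is named.

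The timing is as follows.

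- **Biology, long term.** Section 3 sets the first recording as follows: "all biological measures will be administered at the baseline visit 10 minutes before using the device". For the period after that visit it schedules a single repeat: "then again one time at the 8 week follow-up visit". The procedure text in Section 6.1.1 repeats self-report, biological and blood measures together at 8 weeks. Section 9.3.1 fixes the non-inflammatory contrast as first baseline time point to week 8.
- **Symptoms.** The self-report scales are taken at baseline and week 8. The CAPS is taken at screening and week 8 (Table 1 in Section 6.1.1).
- **In between.** Section 10.1.6 describes one coordinator phone call at week 4. No symptom scale or biologic measure is attached to it.

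The design is small: "The total sample size for the Aim 2 pilot trial is 30 World Trade Center Health Program responders with PTSD", and "Responders will be randomly assigned in a 2:1 ratio to either taVNS or sham". Section 8.1 (Potential Limitations) looks ahead to "an RCT with a large sample size powered to detect differences in outcomes and mediational relationships". The cautions in Sections 8.1 and 9.3.1 concern the size of effects estimated in a small pilot. They do not mention the direction of a biology-symptom relation.

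**The concern.** Mediation is a directional causal claim: taVNS changes the biomarker, and the biomarker changes symptoms. When the biomarker and the symptoms are each observed once after treatment, at the same visit, the opposite order fits the data equally well: taVNS changes symptoms, and the biomarker follows. Randomisation protects the comparison between arms. It does not order two variables that are both measured after randomisation. No later choice of model can supply that order, so this is a matter of measurement schedule and not a detail that an analysis plan could settle.

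The pilot is meant to hand potential mediators to a larger RCT (Sections 1.1 and 3). A biomarker that only tracks recovery could be carried forward as a mechanism.

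**Working it through.** **1. The plan's own figure.** No figure is given for mediation. The only statistical figure is Table 2: "We calculated two-sided 95% confidence intervals for one proportion using the Clopper-Pearson method" at n = 30. With x = 30p and beta quantiles, all six rows reproduce to three decimals (for example p = 0.90 gives 0.735 to 0.979). Table 2 says nothing about mediation.

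**2. Inputs.** From the documents: 30 participants at 2:1 gives 20 and 10. Section 9.1 expects the following: "Our primary outcome measures are expected to be 75% for recruitment, 90% for retention, and 80% for adherence". At 90% retention, 0.9 × 20 = 18 and 0.9 × 10 = 9 complete. The arm difference d and the within-arm correlation rho are not in the documents. They are assumed here: d = 0, 0.5 and 0.8 SD, and rho = 0.3, 0.5 and 0.7.

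**3. Algebra under pure reverse causation.** Let A be arm, Y symptom change (improvement positive) and M the biomarker, with no effect of M on Y:

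- Y = d·A + e, with var(e) = 1
- M = rho·Y + √(1 − rho²)·u, with var(u) = 1

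Within arm, Y and M each have variance 1 and correlation rho. The product-of-coefficients analysis then gives:

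- a (M on A) = rho·d
- b (Y on M, given A) = rho
- indirect effect a·b = rho²·d; total effect = d; apparent mediated share = rho²

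So the share is 0.09, 0.25 and 0.49 at rho = 0.3, 0.5 and 0.7, although the true share is 0. Sample size does not enter.

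**4. Simulation check (2,500 runs per cell).** Joint significance means that both a and b have p < 0.05, two-sided.

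| Arms | d | Apparent share at rho 0.3 / 0.5 / 0.7 | Joint significance |
|---|---|---|---|
| 20 v 10 | 0.5 | 0.091 / 0.245 / 0.489 | 2% / 8% / 14% |
| 20 v 10 | 0.8 | 0.093 / 0.245 / 0.492 | 3% / 12% / 28% |
| 18 v 9 | 0.5 | 0.091 / 0.247 / 0.487 | 1% / 6% / 13% |
| 18 v 9 | 0.8 | 0.088 / 0.246 / 0.497 | 3% / 11% / 27% |
| 200 v 100 | 0.5 | 0.090 / 0.250 / 0.490 | 23% / 53% / 82% |
| 200 v 100 | 0.8 | 0.089 / 0.250 / 0.487 | 48% / 91% / 99.5% |

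The share does not move with sample size. The chance of calling it significant does. With d = 0 the indirect effect averages about 0, and joint significance is 2% to 5% at 20 v 10.

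**5. Spread at the planned size.** At 18 v 9, d = 0.8 and rho = 0.5, the expected false indirect effect is 0.25 × 0.8 = 0.20 SD. Over 20,000 runs the central 95% of estimates ran from about 0.7 SD in the direction of mediation to about 0.2 SD the other way, and 83% pointed towards mediation. Power for the total effect itself at 20 v 10 is 25% (d = 0.5) or 54% (d = 0.8).

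**6. Is there a biologic measure that precedes week-8 symptoms?** The passages disagree.

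| Item | One account | Other account |
|---|---|---|
| Non-invasive recordings at baseline | Before the device only: Sections 1.1, 3, 8.1 and 6.1.1 (Procedure) | Before, during and after the first session: Table 1 |
| Blood draws | Two in all, one at baseline: Section 2.3.1; before the device and at week 8: Section 3 | Before and after the first session, plus follow-up: Table 1 and Section 8.1 |
| Last blood draw | 8 weeks: Sections 3, 6.1.1 (Procedure) and 8.1 | 6 weeks: Table 1 |

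Sections 8.1 and 9.3.1 also promise within-subject correlations of acute and long-term measures, which need the acute recordings to exist. No stressor or trauma-cue task is described anywhere.

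**The case against.** The strongest reply is that the analysis is exploratory and tertiary, that no primary or secondary endpoint depends on it, and that finding candidates for a later RCT is what a pilot is for. Looking now and powering later is also coherent. A reader might take the reference to a later RCT powered for mediational relationships as an admission that mediation cannot be explored here, but the text does not say that. All of this stands and keeps the point minor. It does not answer the question of direction, because the stated cautions cover only effect size.

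A second reply is that no model is fixed, so the product-of-coefficients analysis is an assumption. That is true. But any model fed with week-8 biology and week-8 symptoms lacks the same ordering.

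Three stronger readings are tempting and are not supported:

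- *The trial never measures reactivity.* Table 1 lists recordings during and after the first session, and Table 1 and Section 8.1 list a post-device blood draw. Either could give a response to stimulation. The accurate statement is that the protocol contradicts itself. Relabelling everything as resting measures would settle that conflict by wording alone.
- *Biology and symptoms share the same two visits.* Baseline CAPS is taken at screening. If Table 1's 6-week draw were real, inflammatory markers would come before the week-8 symptoms.
- *A follower biomarker will appear to mediate.* It can. This needs a real taVNS effect and a biomarker-symptom correlation, and at n = 30 sampling noise exceeds the bias.

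**Conclusion.** The concern holds for the long-term biologic measures. On the 8-week schedule given in most of the text, a mediator cannot be distinguished from a consequence of symptom change. Under pure reverse causation with a real taVNS effect, the apparent mediated share is about rho²: 9%, 25% or 49% at assumed rho of 0.3, 0.5 or 0.7, the same at 30 participants as at 300. Joint significance at 20 v 10 is about 2% to 28% under the assumed d and rho, so the likelier harm is a misleading point estimate carried forward than a significant false finding. The algebra is exact for a linear model. The values of d and rho, and the premise that the biomarker is wholly a consequence, are assumptions.

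The acute response around the first session is the one biologic response that would clearly precede week-8 symptoms, and the protocol is inconsistent on whether it is collected. As a tertiary, hypothesis-generating analysis, this is a cheap improvement and no threat to the feasibility conclusions.

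**What to change.** 1. In Sections 8.1 and 9.3.1, replace the mediation sentence. For each biologic measure, report the taVNS-sham difference at 8 weeks, adjusted for its baseline value, with a 95% confidence interval. Describe concurrent week-8 relations between biology and symptoms as association, not mediation.
2. Reconcile Sections 1.1, 2.3.1, 3, 6.1.1 (Procedure) and 8.1 with Table 1 on the during and after recordings, on the number of blood draws, and on 6 versus 8 weeks for the last draw.
3. Define physiological reactivity by what is actually recorded, or drop the term.
4. If the acute recordings are kept, name the acute response at the baseline visit as the candidate mediator to carry forward. Its timing gives it the right order; it does not by itself establish causation.

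The cost is protocol wording and a simpler analysis. If Table 1's acute recordings are what is intended, no data are needed beyond those it already lists. The pilot gives up the claim of mediation for concurrent measures.
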